3.2 Research Design and Methods

This is an 8-week, randomized, open-label trial to evaluate the hemostatic efficacy of rVWF plus TA vs. rVWF alone to prevent postpartum hemorrhage, measured by quantitative blood loss (QBL) at delivery in women with VWD. We hypothesize that while rVWF is a hemostatic agent indicated for prevention and treatment of bleeding, including surgical bleeding and delivery, the physiologic fibrinolysis that occurs within three hours of delivery may contribute to an enhanced bleeding tendency in women with VWD and to their greater risk of PPH. We therefore propose to use tranexamic acid, an antifibrinolytic agent, together with rVWF to determine if the combination reduces PPH. It is anticipated that 20 subjects who meet eligibility criteria will enroll in and complete this study. All aspects of this study, including the rVWF infusion, screening, biologic effects study by von Willebrand tests (VWD profile), are considered experimental. This pilot study is an inpatient and outpatient study and will last up to 2 years. The duration of the study for each subject will be up to 8 weeks. With the exception of the screening visit (32-39 weeks' gestation) and the final visit (day 21 postpartum) at either the Hemophilia Center of Western PA (HCWP) or Magee Outpatient Clinic, the study will be performed while the subject is an inpatient at Magee Women's Hospital.

Based on the established safety and efficacy of rVWF in individuals with VWD including pregnant women and at childbirth,^{34,35} and very low rate of thrombosis, 0.4%, based on 570 patients in 13 studies,³⁶ and the established safety and efficacy of TA in surgery,¹¹ trauma,¹² and childbirth,¹³ it is anticipated that the proposed doses will be safe and well-tolerated, with no thrombosis, allergic reaction, or adverse effects.

The goal of the current study will be to obtain preliminary information on the safety and efficacy of rVWF given at 80 IU/kg at delivery and day 1, day 2, with or without TA 1 gm IV within 3 hours of delivery in reducing postpartum hemorrhage in 20 pregnant VWD subjects. If the study recruitment, randomization, drug administration, data collection and management are feasible, then the large, multicenter phase III trial will be initiated. As both drugs are FDA-approved and have been previously used in VWD patients without adverse effects, we anticipate none during the study. If any subject experiences any grade 3 or higher treatment-related toxicity, blood loss, allergic reaction (fever, chills, hives, tachycardia, chest discomfort), or thrombosis, the decision to continue the study will be made by a local Data Safety Monitoring Committee.

DOSING SCHEMA

Study Arms	No. Subjects	Study Drug(s) at Delivery	Study Drug Postpartum
Arm A	10	rVWF 80 IU/kg + TA 1 gm	rVWF 80 IU/kg days 1 and 2
Arm B	10	rVWF 80 IU/kg	rVWF 80 IU/kg days 1 and 2

rVWF is a single-dose IV infusion given over 5-10 minutes. TA is a single-dose IV infusion given over 10 minutes.

Screening Procedures. Following informed consent, subjects will be screened at the Hemophilia Center of Western PA, by medical history, physical examination, vital signs (height, weight, blood pressure, respirations, heart rate, temperature), and baseline laboratory studies within 3 weeks of the escalating dose study. Baseline labs will include **VWF assays** (VWF:RCo, VWF:Ag, FVIII:C); **coagulation tests** (fibrinogen, d-dimer), **blood counts** (hemoglobin, hematocrit, platelet count); and **iron tests** (Fe, TIBC, ferritin). All tests will be drawn at screening (32-39 weeks' gestation), and all tests except for the iron tests will be drawn on admission for childbirth, at day 1, day 2, and day 21 postpartum. Blood draws will be performed on day 0 pre-delivery by the Magee Labor and Delivery unit as soon as the IV is started. Subsequent blood draws on day 1 and day 2 will be coordinated through HCWP research team. The total blood draw is 49 cc (~2.5 tbsp), including 13 cc (~1 tbsp) at screening; and 9cc (~0.6 tbsp) at the remaining 4 blood draw draws. See Appendix 1.

Up to 30 subjects will be screened to assure 20 subjects are enrolled. Subjects will be randomized to rVWF + TA vs. rVWF alone at delivery. Subjects will receive only the study drug(s) to which they are

randomized, by slow push intravenous infusion. (See Dosing Schema, above). The dose of rVWF will be 80 IU/kg given intravenously over 5-10 minutes at delivery and on day 1 and day 2 postpartum. The dose of TA will be 1 gm (100 mg/mL) given intravenously at an approximate rate of 1 mL/min within 3 hours of delivery. Subjects on Arm A will receive: rVWF 80 IU/kg IV at delivery and on day 1 and day 2 postpartum plus TA 1 gm IV within 3 hours of delivery. If bleeding continues after 30 minutes of the first TA dose, a second dose of TA 1 gm IV will be given. Subjects on Arm B will receive: rVWF 80 IU/kg IV at delivery and on day 1 and day 2 postpartum. rVWF will be given by IV infusion by the Magee research nurse just before delivery, and day 1 and day 2 postpartum. TA will be given by IV infusion by the Magee research nurse within 3 hours of delivery. Efficacy assessment, quantitative blood loss (QBL) at delivery, will be determined at delivery, and obtained from the medical record. Safety assessments, including lochia blood loss by pictorial blood assessment chart (PBAC), blood products, transfusion, and other medications will be recorded on the patient diary at 1 day, 2 days, and 21 days postpartum. After each infusion at delivery and on day 1 and day 2 postpartum, any symptoms, allergic reaction, or thrombosis will also be recorded.

The total blood draw for the entire study is 49 cc (~3 tbsp), including 13 cc (~1 tbsp) at screening (32-39 weeks' gestation), and 9 cc (~ ½ tbsp) each on admission for childbirth, at 1 day, 2 days and 21 days postpartum. Blood samples collected during this study will be stored indefinitely at the hemophilia Center of Western PA (HCWP). If other studies are planned, the subject will be re-consented for approval. The stored samples will be under the control of [name]. There is no plan to use the samples for genetic tests or other tests nor to make them available to secondary investigators.

Laboratory Assays. One blue top (5.0 cc) will be obtained for VWF assays: VWF ristocetin cofactor by platelet aggregometry, VWF antigen by ELISA, FVIII activity by chromogenic assay on an ST4 analyzer; and coagulation assays: fibrinogen by Clauss method, and d-dimer by quantitative assay run in the ITxM/Vitalant Coagulation Laboratory, Pittsburgh. One purple top (4.0 cc) will be drawn for blood counts (hemoglobin, hematocrit and platelets), and one SST tube (4.0 cc) will be drawn for iron studies (iron, TIBC, and ferritin) to be run by standard methods at UPMC University Clinical Laboratories.

Study Termination. A subject will be terminated from the study if any of the following situations arise: the subject develops grade 3 or higher toxicity, allergic reaction, or thrombosis at any time during study.

Study Visit 1: Screening, 32-39 Weeks' Gestation

This visit will take place prior to infusion of study drug(s) in order to confirm eligibility requirements. The following tests or assessment will be performed at the Screening Visit.

- The PI, [name] or a co-investigator will discuss the study with potential study subjects, answer questions and assure there is adequate time for the potential subject to decide to participate in the study. The potential subject may sign consent or take the consent with them to discuss with family members or other members of the healthcare team. If the potential subject is interested in participating in the study, she may sign the consent document.
- Medical history will include age, all medical diagnoses, current medications, any allergies.
- Vital signs will include blood pressure, temperature, respirations, pulse, weight and height
- Blood draw: a 13 ml (1 tbsp) plasma sample for blood counts and iron studies by UPMC University Clinical Laboratories; and VWF assays and coagulation tests by the ITxM/Vitalant Coagulation Laboratory, Pittsburgh.
- The subject will be randomized and informed of the group to which she is randomized.

Study Visit 2: Admission for Childbirth

This visit begins on admission for childbirth.

- Interim medical history, new diagnoses, medications, allergies.
- Blood draw: a 9 ml plasma sample for blood counts at UPMC University Clinical Laboratories, and VWF assays and coagulation tests by the ITxM/Vitalant Coagulation Laboratory, Pittsburgh.
- Study subject will receive study drug(s) to which they are randomized. Arm A subjects will receive rVWF plus TA, while Arm B subjects will receive rVWF alone. The rVWF is given immediately before epidural or delivery, which is first. TA is given within 3 hours of delivery. If bleeding continues after 30 minutes of the first TA dose (in Arm A), a second dose of TA 1 gm IV will be given.
- Quantitative blood loss (QBL) during C-section and vaginal delivery will be calculated by the labor suite nurse and the mode of delivery will be obtained from hospital medical chart.
- Assessment for adverse events, allergic reactions, thrombosis, other bleeding
- The study subject will be given a Diary, to record lochia blood loss by pictorial blood assessment chart (PBAC), blood products, transfusion, and concomitant medications daily for up to 21 days.

Study Visit 3: Day 1 Postpartum

The visit occurs at 1 day postpartum.

- Blood draw: a 9 ml plasma sample for blood counts at UPMC University Clinical Laboratories, and VWF assays and coagulation tests by the ITxM/Vitalant Coagulation Laboratory, Pittsburgh.
- Interim medical history, new diagnoses, medications, allergies.
- Diary review: lochia blood loss by PBAC, blood products, transfusion, and concomitant medications.
- Assessment for adverse events, allergic reactions, thrombosis, other bleeding

Study Visit 4: Day 2 Postpartum

The visit occurs at 2 days postpartum.

- Blood draw: a 9 ml plasma sample for blood counts at UPMC University Clinical Laboratories, and VWF assays and coagulation tests by the ITxM/Vitalant Coagulation Laboratory, Pittsburgh.
- Interim medical history, new diagnoses, medications, allergies.
- Diary review: lochia blood loss by PBAC, blood products, transfusion, and concomitant medications.
- Assessment for adverse events, allergic reactions, thrombosis, other bleeding

Study Visit 5: Day 21, End of Study Visit

The visit occurs at 21 days postpartum, at the end of study.

- Blood draw: a 9 ml plasma sample for blood counts at UPMC University Clinical Laboratories, and VWF assays and coagulation tests by the ITxM/Vitalant Coagulation Laboratory, Pittsburgh.
- Interim medical history, new diagnoses, medications, allergies.
- Diary review: estimated lochia blood loss by PBAC, blood products, transfusion, and concomitant medications.

- Assessment for adverse events, allergic reactions, thrombosis, other bleeding.

The blood volume for all tests is 49 cc (~3 tbsp) during this 8-week trial.

3.3 Data Collection and Statistical Consideration.

This is a pilot study comparing rVWF + TA vs. rVWF alone in subjects with Von Willebrand disease, and therefore, comparisons between arms will be descriptive, including mean, median, standard deviation, frequency and percentages. A sample size of at least 20 subjects should provide be sufficient to determine feasibility of enrollment, study drug administration, and data collection for a future phase III trial. Data will be collected by [name] and her research nursing staff. All data required by the study will be adequately documented in the source documents (hospital records, clinical and office charts, laboratory reports, subject diaries, pharmacy dispensing records).

The Primary Objective is to determine the efficacy of rVWF plus TA vs. rVWF alone in reducing postpartum hemorrhage in women with VWD. The Primary Endpoint is quantitative blood loss (QBL) at delivery. The Secondary Objectives are to evaluate the safety, tolerability, and mechanism of rVWF plus TA vs. rVWF alone in reducing postpartum hemorrhage in women with VWD.

The Secondary Endpoints include safety assessment by lochial blood loss by pictorial blood assessment chart (PBAC) blood products, transfusion, and hysterectomy within 21 days of delivery; and mechanism of PPH reduction by VWF assays, fibrinogen, and d-dimer with 21 days of delivery.

Analysis of endpoints. The Primary Endpoint is based solely on quantitative blood loss (QBL) at delivery obtained by the labor suite nurse and documented by hospital chart. The Secondary Endpoints are based on assessments of safety and the mechanism of hemostasis by rVWF and/or TA. Safety variables, including lochial blood loss by PBAC, blood products, transfusions, and other medications; and the mechanistic variables, including VWF assays (VWF:RCo, VWF:Ag, FVIII:C) and coagulation assays (fibrinogen and d-dimer) will be assessed at 1 day, 2 days, and 21 days postpartum, and where possible, compared with assessment at screening.

Descriptive statistics will be provided for the primary efficacy variable and secondary safety and mechanistic assessment variables, and also by treatment arms. The frequency distribution of the hemostatic and safety efficacy assessments will be presented for each of the study arms.

Blood Sample Storage. Blood samples will be stored indefinitely at the Hemophilia Center of Western PA under the control of [name]. Samples will be labeled with code numbers, and information linking the code numbers to the subjects' identities will be kept in a separate, locked file at the Hemophilia Center.

Adverse events. The analysis of adverse events, including allergic reaction, thrombosis, and other bleeding, will be based on the number of subjects with adverse events, and incidence rates will be calculated as the number of subjects with an event divided by the number of subjects exposed to drug. Subjects with multiple events will be counted only once in the numerator. For analysis, the highest-grade severity will be considered, and for analysis of duration, the multiple episodes will be summed. Adverse events will be summarized, and each event reported by a subject will be counted repeatedly. The corresponding incidence rates for adverse event episodes will be calculated by the number of adverse event cases over the number of doses. Adverse event incidence rates will be categorized by body system, relationship to study drug, severity of adverse event, age, sex, time of onset of adverse event, and duration of adverse event. Laboratory variables will be analyzed by descriptive statistics.

Sample Size and Power for Pilot Study

Pilot studies require a minimum of nine subjects to prevent an unnecessarily high number of subjects to receive a study drug, but a high enough number to provide insight into safety and efficacy parameters for a study drug.⁴¹ The minimum planned sample size of 20 evaluable subjects also provides adequate power to

evaluate the success and feasibility of the study.⁴¹ The study is considered successful if treatment of fewer than or equal to 6 of the 20 subjects is assessed ineffective or unsafe. The study is considered feasible if procedures, i.e. recruitment, randomization, and study drug administration can be performed successfully.

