There will be no cold calling. The Site PI will determine the patient’s interest in study participation, and, if the patient is interested, the study will be discussed in further detail and the informed consent reviewed. Subjects will be encouraged to take time to decide on participation and ask questions. If subjects decide to take a consent form home for further viewing, discussion will include the purpose, safety issues, and risks and benefits of the study. All questions will be answered prior to and obtaining informed consent. No experimental procedures or interventions will occur until after informed consent is obtained. The investigator’s certification statement will be signed at the time consent is obtained. If any new information occurs during the conduct of the study, subjects who have been consented will be informed and will be re-consented with this information at the next visit. A de-identified prescreening/ screening log will be kept, and all reasons for exclusion documented in study source documents and screening log. Subjects who read the consent form are free to refuse enrollment, and participants will be free to withdraw at any time. If subjects wish to withdraw, they may do so by addressing a letter to the principal investigator. Any data collected prior to the time of withdrawal will continue to be used, but no additional information will be collected. Processed blood sample results will continue to be used for the research study; however, remaining samples will be destroyed or used as indicated by subject’s letter. The reason (e.g. AE, lost to follow-up, etc.) and date of withdrawal for all subjects withdrawn from this study will be recorded. Subject information obtained by electronic data capture will be stored and managed on the GSPH Data Center website. The IRB may inspect the records of this study. Every effort will be made to keep the subject’s personal medical data confidential.

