In addition to halting enrollment and further treatment, such an event will be handled as a serious adverse event (SAE) and reported in an expedited time frame to the FDA. The data concerning the event and subject with input from the site HTC Co-Investigator will be reviewed by the DSMC along with all other available data to determine appropriate follow-up, with a decision to continue enrollment and treatment of subjects at that time. If the decision is made to discontinue the study, the Co-Investigators will be notified and the appropriate final study evaluations (Final Visit) will be performed on all subjects enrolled in the study at that time.

Additionally, the following may also stop further subject enrollment and treatment.

- The DSMC warrants temporary suspension of enrollment for further review of data generated to date.
- The PI determines that a medically important event warrants further evaluation by the DSMC. In these cases the required follow-up as determined by the PI and/or DSMC will be performed. The DSMC will determine if it is appropriate to reinitiate enrollment in the study. The IRB will be informed of such decisions.

Local Adverse Event Reporting

All adverse events experienced by study subjects from the time of dosing until 30 days after administration is to be recorded on the CRF, regardless of the severity of the event or its relationship to study treatment.

The serious AE reporting procedures are based on the “Cancer Therapy Evaluation Program: Common Terminology Criteria for Adverse Events” (CTCAE) v 4.03, June 14, 2010.⁴⁰ Subjects will report to HTC co-investigator or to the HTC nursing coordinator, any AE or SAE. AE's will be classified as mild (does not interfere with routine activities), moderate (interferes somewhat with routine activities), or severe (impossible to perform routine activities). The following algorithm will be used to assess the causality of all AE's:

- Not related: The event can readily be explained by factors not involving rVWF and/or TA, and a temporal relationship with rVWF and/or TA, does not exist.
- Possibly related: A clinical event, including laboratory test abnormality, with a reasonable time sequence to administration of rVWF and/or TA, but which could also be explained by concurrent disease or other drugs or chemicals. Information on drug withdrawal may be lacking or unclear.

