- Probably related: The temporal relationship between the administration rVWF and/or TA is compelling, and the event cannot be explained by the subject's medical condition or other therapies.
- Related: The event follows a reasonable temporal sequence from administration of rVWF and/or TA follows a known or suspected response pattern to rVWF and/or TA, is confirmed by improvement upon stopping the agent (de-challenge) and reappears upon repeated exposure to rVWF and/or TA.

All AEs, regardless of severity, will be followed up by HTC Investigator until satisfactory resolution. All subjects experiencing AEs will be monitored until symptoms subside and any abnormal laboratory values have returned to baseline, or until there is a satisfactory explanation for the changes observed, or until death, in which case a full pathologist's report will be supplied, if possible. Withdrawal from the clinical study and therapeutic measures shall be at the discretion of the investigator.

As required by the University of Pittsburgh Institutional Review Board, if there is an unexpected, serious internal adverse event (life threatening or fatal) that is determined to be associated with rVWF and/or TA, it will be reported to the IRB within 24 hours. If the event is not serious, unexpected or related to either agent, it will be reported within 5 days. External adverse events that are unexpected, related to either agent and determined to place the subject at greater risk than previously recognized, will be reported within 10 working days of notification.

Adverse Event (AE) Reporting at sites:

All events must be assessed to determine the following:

- If the event meets the criteria for an SAE
- The relationship of the event to study treatment
- The severity of the event

An AE is any untoward medical occurrence in a subject in whom a pharmaceutical product is administered and that does not necessarily have a causal relationship with this treatment. An AE can therefore be any unfavorable and unintended sign (including an abnormal laboratory finding), symptom, or disease temporally associated with the use of a pharmaceutical product, whether or not related to the pharmaceutical product.

A serious adverse event (SAE) is any untoward medical occurrence that at any dose:

- results in death

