- in the view of the Investigator, places the subject at immediate risk of death (a life-threatening event), but does not include an event that, had it occurred in a more severe form, might have caused death
- requires inpatient hospitalization or prolongation of existing hospitalization
- results in persistent or significant disability/incapacity, or
- results in a congenital anomaly/birth defect.

An SAE may also be any other medically important event that, in the opinion of the Investigator, may jeopardize the subject or may require intervention to prevent one of the other outcomes listed in the definition above. (Examples of such medical events include allergic bronchospasm requiring intensive treatment in an emergency room or convulsions occurring at home that do not require an inpatient hospitalization.)

In this study, the following events are considered medically important and must be reported as SAEs:

- A subject develops other bleeding in association with administration of rVWF and/or TA.
- A subject develops anaphylaxis in association with administration of rVWF and/or TA.
- A subject develops a thrombotic event in association with the administration of rVWF and/or TA, with the exception of intravenous (IV) infusion site thrombophlebitis.
- A subject develops a Grade 2 or greater allergic reaction in association with administration of rVWF and/or TA defined as follows using the CTCAE Evaluation.
 - Grade 2 Transient flushing, rash, or drug fever $\geq 38^{\circ}\text{C}$.

- Grade 3 Symptomatic bronchospasm; with or without urticaria; parenteral medication(s) indicated; allergy-related edema/angioedema; hypotension
- Grade 4 Anaphylaxis

Any SAE experienced by the subject from the time of dosing until 30 days after rVWF and/or TA administration is to be recorded on an SAE Form, regardless of the severity of the event or its relationship to study treatment. SAEs must be reported to the PI. Any SAE ongoing when the subject completes the study or discontinues from the study will be followed by the Investigator until the event has resolved, stabilized, or returned to baseline status.

A serious pre-treatment event associated with the conduct of the study experienced by the subject after signing the ICF, but before administration of study treatment is to be recorded on the Serious Adverse Reaction (SAE) CRF and faxed (and electronically uploaded) to the PI within 24 hours of the study site staff becoming aware of the event.

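### Safety events end a woman's study participation, not just her study drug, and nothing requires her remaining scheduled PBAC, diary and assay data

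*Combined protocol and SAP*

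**What the plan says.** The Study Termination paragraph of Section 3.2 reads "A subject will be terminated from the study if any of the following situations arise", and the triggers are that "the subject develops grade 3 or higher toxicity, allergic reaction, or thrombosis at any time during study".

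Dosing ends early. TA is given within 3 hours of delivery, with a second dose if bleeding continues, and the last scheduled rVWF dose is on Day 2 (Section 3.2). Collection runs longer. Section 3.3 and the Schedule of Events place the PBAC, diary review, VWF assays, fibrinogen and d-dimer at Days 1, 2 and 21, and the Study Visit 2 text has the diary kept daily for up to 21 days.

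Other text bears on what follows such an event:

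- Section 3.2, before the Dosing Schema: after an event of this kind in any subject, "the decision to continue the study will be made by a local Data Safety Monitoring Committee".
- Section 5.0: adverse events and SAEs are recorded to 30 days after administration. Women with adverse events are monitored until abnormal laboratory values return to baseline or are explained. "Any SAE ongoing when the subject completes the study or discontinues from the study will be followed by the Investigator".
- Section 5.0: the DSMC reviews data on all enrolled subjects on an ongoing basis. Where the DSMC suspends enrolment or the PI refers an event, "the required follow-up as determined by the PI and/or DSMC will be performed".
- Section 5.0, if the whole study is discontinued: "the appropriate final study evaluations (Final Visit) will be performed on all subjects enrolled in the study at that time".
- Section 5.0, on adverse events: "Withdrawal from the clinical study and therapeutic measures shall be at the discretion of the investigator".
- Section 4.5, on a woman's own withdrawal: "Any data collected prior to the time of withdrawal will continue to be used, but no additional information will be collected".

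**The concern.** Stopping a drug protects the woman. Ending her study participation adds no protection once dosing is complete, yet the rule applies throughout the study. For an event on Days 3 to 21 there is no scheduled dose to withhold, so the rule's only effect is on participation.

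The measures left exposed are named secondary endpoints: lochial loss by PBAC, diary-recorded blood products and transfusion, and the mechanism assays. If they go missing, it is because a safety event occurred, so the gap is informative and the arm summaries tilt towards women without events. A descriptive analysis does not remove that tilt, because a mean or frequency that omits such women is still selective. Each arm has 10 women, and Section 3.3 names data collection among the feasibility questions the pilot should answer.

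**Working it through.** The documents give no figure to reproduce on this point. The check is a reading of the follow-up provisions, then a sizing.

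**Does any provision require the scheduled assessments after an individual termination?**

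- Adverse event and SAE recording and follow-up (5.0): protects event data and monitors abnormal laboratory values. It does not call for the PBAC, the diary or the Day 1, 2 and 21 draws.
- DSMC review (5.0): covers all data collected, but does not say what must be collected after termination.
- Follow-up set by the PI or DSMC (5.0): could include these measures, but names none of them.
- Final Visit (5.0): tied to stopping the whole study, not to one woman leaving it.
- Withdrawal by the woman (4.5): collection stops, but the text concerns her own decision.
- Allergic reaction and clot management (4.6): describes stopping drug or treatment and is silent on study status.
- Investigator discretion over withdrawal (5.0): sits uneasily with the mandatory wording in 3.2, but creates no duty to collect.

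None does.

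**What one termination exposes.** Inputs: 10 women per arm (Dosing Schema) and 3 postpartum assay sets each (Days 1, 2, 21), so 10 × 3 = 30 sets per arm. The screening and admission sets precede dosing and are unaffected.

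- Event on Day 0 after delivery: 3 sets, 3/30 = 10%, plus all three PBAC and diary reviews.
- Event after the last dose and the Day 2 assessment: 1 set, 1/30 = 3.3%, plus the Day 21 review and the remaining diary entries.

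**How often.** With n = 20 and event rate p, the expected number is n × p and the chance of at least one is 1 − (1 − p)^n.

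- Thrombosis at 0.4% (3.2): 20 × 0.004 = 0.08; 1 − 0.996^20 = 7.7%. Sections 2.1 and 4.6 (Risk Benefit Ratio) put the rate below 0.4%, so 0.08 is closer to a ceiling.
- Thrombosis below 0.001% (4.6, Risk of Thromboembolism): fewer than 20 × 0.00001 = 0.0002.
- Allergic reaction below 0.001% per drug (4.6), with 20 women on rVWF and 10 on TA: fewer than 30 × 0.00001 = 0.0003. Added to 0.08 this gives 0.0803, and the chance of any stays at 7.7%.
- Grade 3 or higher toxicity: no rate is given. If all triggers combined had a rate of 1%, 5% or 10% (an assumed range), the expected terminations are 0.2, 1 and 2, and the chance of at least one is 18%, 64% and 88%. One termination is expected only at 1/20 = 5%.

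At 0.08 women, even if every event fell on Day 0, the expected exposure is 0.08 × 3 = 0.24 of the trial's 60 postpartum assay sets, or 0.4%.

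**The case against.** The strongest reply is that the termination paragraph never says collection stops, that much follow-up plainly continues, and that the numbers are tiny. Most of this stands. The primary endpoint is taken at delivery from the hospital chart, adverse events are still recorded and followed, inpatient transfusions may be recoverable from hospital records, and the success criterion in Section 3.3 could be scored from the terminating event itself. D-dimer measured after a thrombosis also reflects the clot and its treatment, so that retained value is worth less.

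Some stronger readings are tempting and are not supported:

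- A reader might infer that the rule necessarily loses the data. The only sentence ending collection (4.5) concerns a woman's own withdrawal, and SAE follow-up continues after discontinuation. The data are not required; they are not forbidden.
- A reader might infer that an event unrelated to study drug reaches the DSMC only through the PI. Section 5.0 has the DSMC review all data on all subjects and lets it suspend enrolment itself.
- A reader might count lost diary days and report large percentages. Sections 3.2 and 3.3 assess these variables at Days 1, 2 and 21, so after the last dose one scheduled assessment is at stake.
- A reader might see Section 4.6 as contradicting the rule. It describes stopping treatment and does not address study status.

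The wording is also ambiguous. It is unclear whether the grade threshold qualifies all three triggers, and whether toxicity must be treatment-related, as it must in the paragraph before the Dosing Schema. The point holds on each reading; only the frequency changes.

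**Conclusion.** The point holds, at minor severity. The protocol ends a woman's participation for these events at any time, including after dosing is complete, and no provision requires her remaining scheduled PBAC, diary and assay assessments. Secondary safety and mechanism data may therefore be missing because of a safety event.

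The likely impact is small on the thrombosis and allergy rates the protocol gives. It rests on two things the documents leave open: the rate of grade 3 or higher toxicity, and how staff would treat collection after a termination. The comparisons are descriptive and the primary endpoint is largely unaffected, so no main conclusion of the pilot turns on this.

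**What to change.** Reword the Study Termination paragraph so that these events discontinue study drug, leaving the choice of which drug to clinical judgement. Then add text such as: *Every randomised woman remains in scheduled collection (PBAC, diary, and Day 1, 2 and 21 assays) to Day 21 unless she withdraws consent or a procedure is judged unsafe. She is summarised in her assigned arm, and values obtained after the event are flagged.* Flagging lets a reader see which values reflect the event or its treatment as well as the assigned regimen. The sentence on investigator discretion in Section 5.0 should be aligned with the new wording.

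The cost is one reworded sentence and a short addition. For an affected woman the burden is the diary and at most 3 × 9 = 27 cc of blood, all within the 49 cc already planned and at visits already scheduled. Protection is not weakened, because study drug is still stopped.
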